### **Serum hepatic fibrosis indices**

Serum hepatic fibrosis indices (including FIB-4, APRI, and NFS) will be determined at Screening, Baseline, and Months 6 and 12 in Part 1, and at Screening, Baseline, Months 6 and 12, and every 12 months thereafter in Part 2.

APRI is calculated using the formula:

$$\text{APRI} = (\text{AST level [ULN]} / \text{platelet counts [10}^9\text{/L]}) \times 100$$

An APRI index of  $\leq 0.50$  indicates the absence of significant fibrosis and an index of  $> 1.50$  indicates the presence of significant fibrosis.

NFS is a validated simple scoring system consisting of routinely measured and readily available clinical and laboratory data to categorize NAFLD patients with and without advanced fibrosis:

$NFS = -1.675 + 0.037 \times \text{age (years)} + 0.094 \times \text{BMI (kg/m}^2\text{)} + 1.13 \times \text{IFG/diabetes (yes = 1, no = 0)} + 0.99 \times \text{AST/ALT ratio} - 0.013 \times \text{platelet (}\times 10^9\text{/L)} - 0.66 \times \text{albumin (g/dL)}$ . FIB-4 is a noninvasive hepatic fibrosis index score combining standard biochemical values, platelets, ALT, AST, and age that is calculated using the formula:

$$\text{FIB-4} = (\text{Age [years]} \times \text{AST [U/L]}) / (\text{platelets [10}^9\text{/L]} \times (\text{ALT [U/L]})^{1/2})$$

A FIB-4 index of  $< 1.45$  indicates no or moderate fibrosis and an index of  $> 3.25$  indicates extensive fibrosis/cirrhosis.

The Enhanced Liver Fibrosis (ELF™) Test is a blood test that provides an ELF Score that delivers information on liver fibrosis severity and will be assessed in this study. The ELF Score is determined by combining in an algorithm, quantitative measurements of by-products of the fibrotic process (hyaluronic acid [HA]), amino-terminal propeptide of type III procollagen [PIIINP]), tissue inhibitor of metalloproteinase 1 [TIMP-1]).

The ELF Score will be determined at Baseline, Month 6, Month 12, and every 12 months thereafter.

The authors analyzed routine demographic, clinical, and laboratory variables to predict presence or absence of advanced fibrosis. Age, hyperglycemia, BMI, platelet count, serum albumin, and AST/ALT ratio were found to be independent indicators of advanced liver fibrosis, so these 6 variables were included in the NFS scoring system. A low cut-off score of -1.455 indicates the absence of advanced fibrosis and a high cut-off score of 0.676 indicates the presence of advanced fibrosis.

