Time-to-event (Part 2: primary endpoint)	Treatment Period	
 All subjects in mITT analysis set included. Any available adequate liver biopsy after baseline will be used for assessment of components of the clinical endpoint that require a biopsy, no matter when obtained. Subjects with multiple liver biopsies will be included as an event if any (one or more) biopsy meets the definition of the primary endpoint, as determined by the adjudication committee. Subjects who do not have an evaluable liver biopsy at both Screening and post-baseline will be included in the analyses as having an event only if they meet a component that does not require a biopsy; otherwise they will be included as not having an event and censored at the last visit. Subjects with partial follow-up data will be included as an event if they meet the criteria for any component of the primary efficacy endpoint, and as a nonevent if they do not meet the criteria for any component. A sensitivity analysis assuming data are missing not at random will be reported. An additional sensitivity analysis imputing an event at the time of censoring will also be reported, although it is anticipated that this analysis will not be informative unless many subjects discontinue due to unobserved NASH progression, which cannot be known.
CFB ANCOVA	Months 6 and 12 in Part 1, and Month 12 and annually thereafter in Part 2 (Month 6 in Part 2 for some endpoints)	
 If missing covariates (including baseline if applicable) 
 Subject excluded Observed data for mean absolute change and relative change from baseline to the times specified in the endpoints will be analyzed. There is no imputation for missing data.
Multiple imputation (Part 1: primary efficacy endpoint)	Month 12 MAR and MNAR	
A sensitivity analysis for the primary efficacy analysis in Part 1 will use multiple imputation to investigate the impact of missing data under a Missing At Random (MAR) assumption. For this analysis, the Month 12 biopsy results will be imputed for the subjects who do not have an evaluable biopsy after baseline. The imputation model will be defined before Part 1 unblinding to avoid the addition bias.
 
The multiple imputation model will use the MI procedure in SAS, using code such as the following:
 <pre>proc mi data=<inputdsn> seed=1305417 nimpute=100 out=<outputdsn>; class outcome trt; var trt <explanatory> outcome;</pre>

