Occasional bridging fibrosis (< 50% linkage of portal and/or central zones)	3																
Marked bridging fibrosis (> 50% linkage of portal and/or central zones but not yet cirrhosis)	4																
Early or incomplete cirrhosis	5																
Established or advanced cirrhosis	6																

[figure not shown]

Baseline assessments for applicable efficacy endpoints defined as follows:

Table 5-13 Efficacy Endpoint Baseline Definitions

Type of Endpoint	Description	Timing
Part 1: Primary, secondary [REDACTED] Improvement of fibrosis stage (NASH CRN system) on liver histology at Month 12 relative to the Screening biopsy	Fibrosis stage (NASH CRN system) based on Screening biopsy	Screening biopsy result before Baseline visit and before subject is randomized
Part 1: Primary, secondary [REDACTED] Worsening of steatohepatitis (no worsening of lobular inflammation or hepatocellular ballooning grade 2005) on liver histology at Month 12 relative to the Screening biopsy	Steatohepatitis status (lobular inflammation or hepatocellular ballooning grade 2005) based on Screening biopsy	Screening biopsy result before Baseline visit and before subject is randomized
Part 1 and Part 2: Change in baseline in noninvasive assessments of liver fibrosis (FIB-4, APRI, NFS, and ELF score)	Occurs within 3 months before the Baseline visit. Baseline visit is defined as the last available assessment before the date of 1 st dosing (for all efficacy and safety endpoints).	Screening serum hepatic fibrosis indices
Part 1 and Part 2: Change in baseline in noninvasive assessments of liver fibrosis (liver stiffness)	The Screening value (if not performed by TE within 6 months prior to the first day of Screening) will be used as the Baseline value. TE will be performed at Baseline if not performed within 6 months prior to the first day of Screening.	Screening via TE or liver imaging

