5.1.1.4 Safety Analyses

Safety analyses will be based on the Safety Population.

No statistical hypotheses are prespecified for safety endpoints (e.g., incidence of AEs, including MACE and T2DM, clinical laboratory evaluations, vital signs, ECGs, biomarkers). Analyses will be primarily descriptive, with any p-values post-hoc and any comparative conclusions requiring confirmation.

Baseline assessments for applicable safety endpoints defined as follows:

Table 5-15 Safety Endpoint Baseline Definitions

Parameter	Description	Timing
Clinical laboratory evaluations, Vital signs, ECGs	Baseline assessment will be the last available value before the first dose of study drug for each parameter	Last non-missing assessment before first dose of study drug

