6.1.1 Analysis Days

Treatment days are defined as follows:

Table 6-1 Analysis Day Definitions

Term	Description
Treatment Day	Relative to treatment start date If analysis date \geq treatment start date: 
• Day = analysis date – treatment start date + 1
○ Day 1 = treatment start date If analysis date < treatment start date: 
• Day = analysis date – treatment start date
○ Day -1 = day before treatment start date○ There is no Day 0

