6.2 Analysis Visit Windows

6.2.1 Efficacy

The analysis visit windows for efficacy endpoints, including liver biopsy, are defined as follows:

Table 6-2 Efficacy Analysis Visit Definitions

Analysis Phase	Analysis Visit (Derived)	Study Visit (eCRF)	Window
Part 1 & Part 2			
Pretreatment	Baseline	Day 1	Treatment Day ≤ 1 , pre-randomization in Part Y
Treatment	Month 12	Day 360	Treatment Day [316, 405], post-randomization in Part 2 Note: For the primary efficacy analysis in Part 1 using the mITT analysis set, any available liver biopsy after randomization will be used for the Month 12 biopsy, no matter when it was obtained relative to the first dose of study drug. Subjects with multiple liver biopsies will have the evaluable biopsy closest to the Month 12 visit included in the analysis.
	Month 60	Day 1800	Treatment Day [1756, 1845], post-dose in Part 2
	End of study	Final or termination visit	Last non-missing assessment during the Treatment Period in Part Y / between Treatment Day 1 in Part Y, post-dose, and Off-treatment Day 1, inclusive, where Y=1, 2.

The following general conventions for repeated or unscheduled assessments will apply unless otherwise specified:

- For scheduled and unscheduled assessments, if more than one assessment is measured within the same visit window, then the record with the latest visit date (from baseline) will be used for that visit window.
- All assessments will be included in respective listings.

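### The SAP Table 5-13 baseline row for FIB-4, APRI, NFS and ELF shuts out the Day 1 sample, contradicts three other baseline rules and, read literally, leaves ELF with no baseline in Part 1

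*SAP*

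**What the plan says.** The Table 5-13 row for change in FIB-4, APRI, NFS and ELF (SAP 5.1.1.3) makes three statements:

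- The description opens by placing the assessment in the Screening window: "Occurs within 3 months before the Baseline visit".
- It then gives the rule: "Baseline visit is defined as the last available assessment before the date of 1 st dosing (for all efficacy and safety endpoints".
- The timing cell reads "Screening serum hepatic fibrosis indices".

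Other parts of the plan define baseline differently:

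- SAP Table 6-2, which covers efficacy endpoints, sets the Baseline window as "Treatment Day ≤ 1 , pre-randomization in Part Y". SAP Table 6-1 fixes what that day means: "Day 1 = treatment start date".
- SAP Table 5-15, for clinical laboratory evaluations, vital signs and ECGs, gives "Last non-missing assessment before first dose of study drug".
- Protocol Section 12.4.2.2 takes each laboratory parameter's last value before randomization.

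On sampling, protocol Section 11.2 states for ELF: "The ELF Score will be determined at Baseline, Month 6, Month 12, and every 12 months thereafter". The same section has FIB-4, APRI and NFS determined at both Screening and Baseline.

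**The concern.** The row's rule turns on the calendar date of first dosing, whereas Table 5-15 turns on the dose itself. Because the Baseline visit is Day 1 and Day 1 is the treatment start date, a date rule excludes everything collected at that visit, including blood taken before the first tablet.

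ELF is the case that matters most. The row names it and sends it to Screening, yet the protocol schedule starts ELF at Baseline. A programmer who follows the row finds no ELF value that qualifies. One who follows Table 6-2 finds a usable Day 1 value. The SAP text gives no order of precedence between these tables.

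What is at stake is the change-from-baseline analysis of the noninvasive fibrosis measures. The protocol lists ELF change from baseline to Month 12 among the Part 1 efficacy endpoints (Section 12.3.1.1), and change in FIB-4, APRI, NFS, ELF and liver stiffness among those for Part 2 (Section 12.3.1.2). SAP Section 5.2.2 plans ELF summaries that include change over time.

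**Working it through.** No sample size, power or alpha figure bears on this point. The check applies each written rule to one sample, drawn at the Day 1 Baseline visit before randomization and before the first dose.

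| Rule | Condition | Day 1 pre-dose sample |
|---|---|---|
| SAP Table 5-13 | before the date of first dosing | excluded: sample date equals dosing date |
| SAP Table 6-2 | Treatment Day 1 or earlier, before randomization | accepted: Day 1 ≤ 1 |
| SAP Table 5-15 | before the first dose | accepted |
| Protocol 12.4.2.2 | before randomization | accepted |

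One rule excludes the sample and three accept it.

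**ELF, Part 1.** Protocol Section 11.2 starts ELF at Baseline. SAP Table 6-8 (Section 6.6.2.2) gives Baseline and Months 6 and 12 for the serum fibrosis indices in Part 1, a category that includes ELF. Neither schedules a Screening draw. With Day 1 excluded, no scheduled sample qualifies for any Part 1 subject (1293 randomized, SAP Section 5.2.1).

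**ELF, newly randomized in Part 2.** Table 6-8 lists Screening for the whole index category in these subjects, while protocol Section 11.2 still starts ELF at Baseline. The documents disagree, so the conclusion about ELF is limited to Part 1.

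**FIB-4, APRI, NFS.** Both a Screening and a Day 1 value are scheduled. The row discards the Day 1 value. The Screening visit may fall up to 3 months before Baseline (protocol Section 10.1), so the substitute may be that old. This shift does not depend on the date wording alone, because the row's description and timing cell also point to Screening.

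**What a missing baseline does.** In Table 5-4 the change-from-baseline ANCOVA entry beginning "If missing covariates (including baseline if applicable" excludes the subject, and missing data are not imputed. The descriptive change summaries in Table 5-2 also count only subjects with both a baseline and a post-baseline value. ELF change is therefore lost whichever method is used.

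**The parenthetical.** The row extends its rule to all efficacy and safety endpoints. For laboratory evaluations this contradicts Table 5-15 directly.

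**The case against.** The strongest reply is that this is one loosely worded row among several sound ones. Table 6-2 covers efficacy endpoints and accepts Day 1, Table 5-15 and the protocol do the same, and the SAP's own change summary (Section 8) describes baseline for baseline characteristics as the last assessment before study treatment is given. A sensible programmer would probably use the Day 1 value. Much of this stands: the row is not the SAP's only baseline rule, and the rest of the plan suggests that Day 1 pre-dose was intended. It does not clear the row, which is the endpoint-specific definition, claims general coverage, and points to Screening in its timing as well as its wording.

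A reader might infer more than the documents support:

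- **That inflammation and fasting metabolic markers also lose their baseline.** The row does not name them. The protocol lists fasting metabolic parameters as safety laboratory tests, and the SAP counts biomarkers among the safety endpoints. Table 5-15 keeps the Day 1 pre-dose value for laboratory evaluations. HbA1c is also measured at Screening, and total cholesterol, triglycerides and glucose are in the chemistry panel run then, although its fasting status is not stated.
- **That every subject will lose data.** That follows only if the row overrides every other rule. The visit schedules are not available to confirm the sampling and dosing dates, so no loss rate can be forecast.
- **That regression to the mean biases the comparison.** Screening values help select subjects for biopsy, so within-arm change may be distorted. Selection comes before randomization, however, so the effect is balanced between arms, and the ANCOVA adjusts for the baseline value.
- **That ELF will be analyzed by ANCOVA.** SAP Section 5.2.2 commits only to descriptive statistics for ELF. Table 5-14 plans ANCOVA for continuous secondary endpoints without naming them.

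**Conclusion.** The row is wrong as written and should be corrected. It conflicts with SAP Tables 6-2 and 5-15 and with protocol Section 12.4.2.2. Taken literally, it leaves ELF change from baseline in Part 1 impossible to compute, and moves FIB-4, APRI and NFS to a value up to 3 months old. The cost for those three indices is added noise, which the documents give no means of quantifying, and no bias between arms.

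This rests on one assumption: that the first dose is taken on the date of the Baseline visit. Tables 6-1 and 6-2 and the protocol's use of Day 1 imply it. If a subject's first dose came on a later date, the Baseline sample would satisfy Table 5-13 as well.

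The reach is limited. The Part 1 primary and key secondary endpoints are measured against the Screening biopsy and are not affected. They are the only two tests in the Part 1 hierarchy, so no alpha-controlled conclusion of Part 1 changes.

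**What to change.** Before the Part 1 database lock:

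1. In the Table 5-13 row, define baseline as the last non-missing value before the first dose of study drug, with scheduled Day 1 Baseline samples counted as pre-dose.
2. Change the timing cell to: *Baseline (Day 1); Screening value only if the Day 1 value is missing and a Screening value exists*. This also handles ELF, whichever schedule applies to newly randomized Part 2 subjects.
3. Delete the parenthetical on all efficacy and safety endpoints, or align it with Table 5-15.
4. Use the same pre-dose wording in Table 6-2. It now says pre-randomization, so a Day 1 sample drawn after randomization but before the first dose would pass Table 5-15 and fail Table 6-2.

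The cost is one corrected row and a matching phrase in a second table. No new data, visits or samples are needed.

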### Key Assessments

During Part 1 of the study:

- A Screening visit is to occur within 3 months before the Baseline visit. The informed consent form for Study 3152-301-002 (Parts 1 and 2) and patient education materials about NASH, liver fibrosis, liver biopsy procedures, and study retention tools will be reviewed at the Screening visit.
- As part of Screening, assessment of serum laboratory tests (hematology and chemistry panels), serum hepatic fibrosis indices (non-invasive hepatic fibrosis index score combining standard biochemical values, platelets, ALT, AST, and age [FIB-4]; AST to platelet count ratio index [APRI]; and NAFLD fibrosis score [NFS]) and evaluation of liver stiffness via transient elastography (TE) or liver imaging (performed no more than 6 months prior to the first day of Screening at sites where available) will aid in identifying subjects with clinically significant liver fibrosis prior to proceeding with a new liver biopsy.
- A historical liver biopsy, obtained no more than 6 months prior to the first day of Screening, that meets protocol-required specifications, or a new liver biopsy will be evaluated by an independent central pathologist for all subjects as part of Screening to confirm histologic evidence of NASH and fibrosis Stages 2 or 3.
- Subjects meeting all other eligibility criteria and with suspicion of significant liver fibrosis (through clinical evaluation, hepatic fibrosis indices, and/or liver stiffness assessment [performed no more than 6 months prior to the first day of Screening]) will undergo a new liver biopsy during the Screening period. In randomized subjects, a second post-treatment liver biopsy will be collected at the Month 12 visit ( $\pm 2$  weeks).
- Fasting metabolic parameters, including lipid panel (triglycerides, total cholesterol, high-density lipoprotein [HDL], low-density lipoprotein [LDL], very low-density lipoprotein [VLDL]), glucose, insulin and hemoglobin A1c (HbA1c), will be measured at Baseline and at Months 3, 6, and 12.

- Samples for biomarkers of systemic inflammation, including interleukin (IL)-1 $\beta$ , IL-6, high-sensitivity C-reactive protein (hs-CRP), and fibrinogen will be collected at Baseline and at Months 3, 6, and 12.
- Samples of non-invasive serum hepatic fibrosis indices (FIB-4, APRI, NFS), ELF Score, and PRO-C3 will be collected at Months 6 and 12.

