- At selected sites where available, non-invasive assessment of liver fibrosis by TE will be performed at Baseline (if not performed at Screening), and at Months 6 and 12.
- Pharmacokinetic samples for CVC will be collected at Months 3, 6, and 12 (pre-dose and at least 1-hour post-dose) (see Section 11.7)
- Weight, waist circumference, and hip circumference will be performed at Screening, Baseline and at Months 3, 6, and 12. Height will be performed at Screening.
- Physical examination, vital signs, and laboratory analyses (serum chemistry and hematology) will be performed at each visit. Serum immunoglobulin G (IgG), antinuclear antibody (ANA), anti-smooth muscle antibodies (SMA), anti-liver/kidney microsome type 1 (LKM1) and anti-liver cytosol type 1 (LC1) antibodies will be evaluated at Baseline. Electrocardiograms will be performed at Baseline and at Month 12.
- Adverse events and concomitant medications will be assessed at each visit.

### 7.1.2. Part 2

Part 2 of the study will focus on assessing the effect of CVC on clinical outcomes in approximately 2000 subjects, including up to 1200 subjects with a liver biopsy diagnosis of NASH and Stage 2 or 3 liver fibrosis (by NASH CRN system) previously randomized in Part 1 and an additional 800 adult subjects with a liver biopsy diagnosis of NASH and Stage 3 liver fibrosis (by NASH CRN system) newly randomized 2:1 to receive CVC or placebo in Part 2.

Subjects who remain in Part 1 at Month 12 will continue to be evaluated in Part 2 of the study and will continue the same treatment through the end of Part 2. Individual subject treatment assignments will not be revealed until the completion of Part 2 of the study.

Subjects who enter Part 2 from Part 1 of the study will have study visits every 3 months until Part 2 is completed. Study drug will be dispensed and AEs, concomitant medications, and adherence to study drug will be reviewed at every visit (every 3 months). Safety laboratory assessments will be performed every 6 months through the end of the study.

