At sites where available, liver stiffness will be assessed in fasting subjects by ultrasound TE at Baseline (if not performed within 6 months prior to the first day of Screening), at Months 6 and 12 in Part 1, and annually in Part 2. The Screening value (if performed by TE) will be used as the Baseline value. The visit window will be  $\pm 2$  weeks for all on-treatment TE assessments.

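### SAP Table 5-13 reverses the protocol's condition for using the Screening value as the liver-stiffness baseline, and its wording lets in a value not measured by TE

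*SAP*

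**What the plan says.** **Protocol.** The TE paragraph in Section 11.2 gives two separate rules. One says when to measure: stiffness is assessed "by ultrasound TE at Baseline (if not performed within 6 months prior to the first day of Screening". The other says which value counts: "The Screening value (if performed by TE) will be used as the Baseline value". On-treatment measurements are by TE. Section 7.1.1 (Key Assessments) words the trigger a little differently: "non-invasive assessment of liver fibrosis by TE will be performed at Baseline (if not performed at Screening". The same section provides, at Screening, for "evaluation of liver stiffness via transient elastography (TE) or liver imaging", as an aid to deciding who goes on to biopsy. Section 12.3.1.2 lists change from baseline in stiffness, specified as measured through TE, for all subjects.

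**SAP.** The liver-stiffness row of Table 5-13 (Section 5.1.1.3), which covers both parts, has a description of two sentences. The first selects what serves for baseline: "The Screening value (if not performed by TE within 6 months prior to the first day of Screening) will be used". The second orders a measurement: "TE will be performed at Baseline if not performed within 6 months prior to the first day of Screening". The Timing cell reads "Screening via TE or liver imaging". The row above, for the serum indices, adds a general definition meant to cover efficacy and safety measures alike: the latest assessment available ahead of first dose.

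SAP Section 5.2.2 lists no change to the stiffness baseline, and neither does the summary of changes in Section 8. Section 8 says instead that wording in Section 5.1.1.3 was brought into line with the protocol, and gives the six-month term as its example.

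**The concern.** The protocol's condition is that TE was done. The SAP's condition is that TE was not done in a stated period. A programmer cannot follow both. The SAP sentence looks like a merger of the protocol's two rules, with the clause that triggers a Baseline measurement moved into the sentence that selects the baseline value. That origin is an inference.

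The baseline matters twice in this analysis. Under Table 5-2 it enters the change score and is also the ANCOVA covariate. Under Table 5-4 a subject with no baseline is excluded. The choice of value therefore affects both the estimate and who is analysed. Because follow-up is by TE, a baseline from another imaging method would also compare unlike measurements.

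**Working it through.** No arithmetic applies. The check is to run each kind of subject at a TE site through the protocol rule, the SAP row as written, and the SAP's general rule. An earlier TE here means one done in the six months before the first day of Screening.

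| Case | Protocol 11.2 | SAP stiffness row as written | SAP general rule |
|---|---|---|---|
| 1. Earlier TE exists | A TE value: the earlier one, or a Screening TE if one was done | Condition not met, so the Screening value is not designated; no Baseline TE is ordered either. No baseline named | Latest pre-dose assessment, normally a TE |
| 2. No earlier TE; TE done during Screening | Screening TE | Screening TE. Agrees with the protocol, but a Baseline TE is also ordered | Baseline-visit TE if taken, otherwise Screening TE |
| 3. No earlier TE; Screening by other imaging | Baseline-visit TE | The imaging value. A Baseline TE is ordered but not named as baseline | Baseline-visit TE if taken; otherwise the imaging value |
| 4. No earlier TE; no stiffness measurement at Screening | Baseline-visit TE | The Screening value, which does not exist. A Baseline TE is ordered but not named as baseline | Baseline-visit TE |

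Case 1 assumes that a TE from the preceding six months counts as the protocol's Screening value. Section 7.1.1 supports this, since it allows the Screening stiffness evaluation to date from up to six months before Screening begins.

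Three things follow.

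- The row departs from the protocol in cases 1, 3 and 4, and agrees with it in case 2.
- The general rule gives a TE value in most situations, but it contradicts the row in cases 1, 3 and 4. In case 2 it can also contradict both the row and the protocol, if a Baseline TE was taken as well.
- The general rule places no limit on method. In case 3, with no Baseline TE actually obtained, it would accept the imaging value.

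**The case against.** The strongest reply is that the SAP as a whole supplies a workable baseline. The general definition sits one row higher and is meant to apply across endpoints. The row itself calls for a Baseline TE when there is no earlier one. Together they give most subjects at TE sites a TE baseline. This stands as a limit on the practical effect. It does not remove the conflict, because a row with its own specific rule would ordinarily be programmed as written, and the general rule does not require TE.

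A second reply is that the imaging phrase is the protocol's own. That is correct, and the phrase alone is no evidence of a reversed rule. In the protocol, however, it describes a Screening aid, whereas the SAP puts it in the cell that fixes the timing of a baseline for TE follow-up.

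A third reply reads the SAP sentence as meaning the Screening-visit value when there is no earlier TE. That still names nothing in case 1 and leaves two candidates wherever a Baseline TE is also taken.

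Parts of Section 5.1.1.3 are not visible in the public copy, so a fuller TE definition may exist there. The point is therefore about this row, not about everything the SAP says.

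A reader might infer that every subject with a Screening TE loses a baseline, that the baseline is undefined throughout, or that the stiffness results would be uninterpretable. The documents do not support this. Case 2 subjects receive the same baseline from the row as from the protocol, and the general rule and the ordered Baseline TE cover most of the rest.

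**Conclusion.** The point holds as an inconsistency between SAP and protocol in one table row. The condition is reversed. As written, the row names no baseline for subjects with a TE in the six months before Screening. For those with no TE either then or at Screening, it names a value that may be imaging or may be absent.

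Its size is small. It concerns subjects at sites with TE who had a pre-Screening TE or no Screening TE, and neither group's number is given. It affects only change from baseline in liver stiffness, which is outside the testing hierarchy in SAP Sections 5.1.1.3.1 and 5.1.1.3.3. The primary and key secondary endpoints, the alpha allocation and the sample size do not depend on it.

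The conclusion rests on reading the row literally, on the case 1 assumption stated above, and on no contrary rule standing in the blacked-out text.

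**What to change.** Reconcile the stiffness row of Table 5-13 with protocol Section 11.2:

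- Baseline is the TE value from Screening, including a TE done within six months before the first day of Screening; failing that, the TE from the Baseline visit.
- If a subject has more than one pre-dose TE, use the last before first dose, in line with the SAP's general rule. Where a Screening TE is followed by a Baseline-visit TE, this differs from the letter of Section 11.2, so record the choice in SAP Section 5.2.2.
- Strike the imaging alternative from the Timing cell.
- State that a subject with no pre-dose TE has a missing baseline for this endpoint.

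The cost is an edit to one table row and one line in Section 5.2.2, made before database lock and unblinding for Part 1. It needs no new data and no change to study conduct.
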